6.5.10.2 Primary Efficacy

The primary effectiveness analysis will be performed based on the FAS. The primary endpoint is evaluated as the responder status based on subjects' responses to the statement "Clear vision: near, far, and in-between' in the online consumer survey, where a "responder" is defined as a participant agrees the statement. For the primary endpoint, the null hypothesis (H0) is that the proportion of subjects agreeing with the statement (π) is less than or equal to 0.5. The alternative hypothesis (H1) is that the proportion of subjects agreeing is greater than 0.5.

*H*₀:
$$\pi \le 0.5$$

*H*₁: $\pi > 0.5$

The responses to the primary endpoint statement will be summarized using categorical summary statistics (strongly agree, agree, slightly agree, neither agree nor disagree, slightly disagree, disagree, strongly disagree).

Responses of strongly agree, agree, and slightly agree will be coded to a category "Agree." Responses of strongly disagree, disagree, and slightly disagree will be coded to a category "Disagree." The trichotomized responses will be summarized categorically (agree, neither agree nor disagree, disagree).

Neutral responses (i.e., "neither agree nor disagree") will not be included in the primary statistical analysis. The non-neutral responses used for the analysis will be presented using categorical summary statistics (agree, disagree). An exact 95% confidence interval (Clopper-Pearson test) around the proportion of subjects agreeing with the statement will be presented along with the p-value from a one-sided exact binomial test of the alternative hypothesis is that the proportion of subjects agreeing is greater than 0.5.

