6.5.13 Determination of Sample Size

Approximately 300 subjects will be enrolled. Allowing for up to 10% losses, power calculations were completed for 270 completed subjects. An exact binomial test with a nominal 5% one-sided significance level will have 93% power to detect the difference between the Null hypothesis proportion, π_0 of 0.5 and the Alternative proportion, π_1 , of 0.6 when the sample size is 270.

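### Does a one-sided 5% test reported beside a 95% confidence interval make the primary result inconsistent?

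*SAP*

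**What the plan says.** For the primary endpoint, SAP 6.5.10.2 plans an exact 95% Clopper-Pearson interval "around the proportion of subjects agreeing with the statement will be presented along with the p-value from a one-sided exact binomial test". The alternative is that the proportion agreeing exceeds 0.5. Protocol 7.1.1.1 and the protocol synopsis plan the same pair. SAP 6.5.11.1 repeats it for the best-case and worst-case analyses, and SAP 6.5.10.5.1 carries the primary method over to the other consumer-survey statements.

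SAP 6.5.10.2 gives no significance level. The level is in SAP 6.5.13: "An exact binomial test with a nominal 5% one-sided significance level will have 93% power to detect the difference" between 0.5 and an alternative "of 0.6 when the sample size is 270". Protocol 7.8.2 and the synopsis give the same level, and no section gives a different one for this test.

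Three places show what decides success. Protocol 7.1.4.1 sets the hypotheses as a proportion of at most 0.5 against one above 0.5. Protocol 7.1.4.2 and SAP 6.5.11.4 open the supportive tests only if the primary null hypothesis is rejected. The tipping-point steps in SAP 6.5.11.1 judge significance by the p-value. No section makes the interval a criterion.

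**The concern.** A standard 95% Clopper-Pearson interval excludes 0.5 from below exactly when the one-sided exact p-value is at most 0.025. The planned test succeeds at 0.05. The interval that corresponds to that test is the two-sided 90% interval, whose lower end is the one-sided 95% lower limit. The two headline numbers thus work at different error rates, and for some results the p-value would claim success while the interval would not exclude the null.

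The SAP keeps the two aligned elsewhere. For the lens performance ratings (6.5.10.5.6) a two-sided 95% interval goes with a two-sided binomial test. Only the primary endpoint and the analyses that borrow its method pair a one-sided test with the 95% interval.

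If the interval were read as the test, the stated power would be too high for that reading, and a split result would have to be interpreted after the data were seen.

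**Working it through.** **Inputs.** Null 0.5, alternative 0.6, one-sided alpha 0.05 and n = 270, all from SAP 6.5.13. The interval is the 95% Clopper-Pearson interval of SAP 6.5.10.2, taken as two-sided. The SAP does not write that word for the primary endpoint.

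**Formulas.** With X binomial(n, π) and x agreeing:
- one-sided p-value: P(X ≥ x | 0.5)
- lower 95% limit: the 0.025 quantile of Beta(x, n − x + 1)
- lower limit matching a one-sided 5% test: the 0.05 quantile of the same distribution
- power: P(X ≥ critical count | 0.6)

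**The plan's own figure.** At n = 270, P(X ≥ 149 | 0.5) = 0.0501 and P(X ≥ 150 | 0.5) = 0.0387, so the critical count is 150. Power is P(X ≥ 150 | 0.6) = 0.939, against the stated 93%. At one-sided 2.5% the critical count is 152 and power is 0.904, which does not fit. The planned level is therefore one-sided 5%. Enrolment also fits: 270 / 0.90 = 300.

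**Where test and interval part, n = 270.**

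| Agree | Share | One-sided p | 95% interval | Matching lower limit |
|---|---|---|---|---|
| 149 | 55.2% | 0.0501 | 0.490 to 0.612 | 0.49997 |
| 150 | 55.6% | 0.0387 | 0.494 to 0.616 | 0.5037 |
| 151 | 55.9% | 0.0295 | 0.498 to 0.619 | 0.5074 |
| 152 | 56.3% | 0.0222 | 0.5015 to 0.623 | 0.5111 |

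Only 150 and 151 split. The last column agrees with the test throughout.

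**Chance of a split result.** This is P(X ≥ first significant count) − P(X ≥ first count at which the 95% interval excludes 0.5). At n = 270 and a true 0.6 it is 0.9392 − 0.9035 = 0.0357.

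Neutral responses leave the analysis, so n may be below 270. The neutral share is not given. The shares below are assumptions, taken as a fraction of 270.

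| Neutral share | n | Split counts | True 0.50 | 0.55 | 0.60 | 0.65 |
|---|---|---|---|---|---|---|
| 0% | 270 | 150–151 | 1.6% | 9.5% | 3.6% | 0.07% |
| 10% | 243 | 135–137 | 2.8% | 14.7% | 6.9% | 0.24% |
| about 15% | 230 | 128–130 | 2.9% | 15.0% | 7.7% | 0.34% |
| 20% | 216 | 121–122 | 2.0% | 10.2% | 5.8% | 0.33% |

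The chance moves unevenly with n because counts are whole numbers. Over every n from 216 to 270 the split zone is two or three counts wide. The chance there ranges from 3.4% (n = 267) to 8.9% (n = 220) at a true 0.6, and is at most 0.5% at a true 0.65.

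**Error rate of the test.** P(X ≥ critical count | 0.5) is 0.0387 at n = 270, 0.0476 at 243, 0.0495 at 230 and 0.0444 at 216. All are within 5%, whatever interval is shown beside the test.

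**The case for a change.** The strongest case for a change has four parts. The mismatch concerns the primary result. No section says how a split would be read. The zone can widen to three counts once neutral responses are dropped. The worst-case analysis pushes the observed proportion down towards 0.5, where splits occur. A cure would cost one or two sentences: repeat the 5% level in 6.5.10.2 and 6.5.11.1, and add the one-sided 95% lower limit or say that the p-value decides.

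The arithmetic stands, and so does the point that the level appears only in the sample-size text. The rest does not show a defect. The p-value already decides, since the hypotheses, the gate to the supportive tests and the tipping-point steps all rest on the test. An analyst looking for the level finds one value, given the same way in the synopsis, protocol 7.8.2 and SAP 6.5.13. An added lower limit would restate the test: it exceeds 0.5 exactly when the p-value is below 0.05.

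The other remedy, testing at one-sided 2.5%, would match the interval but change a prespecified design choice. At n = 270 it would lower power at 0.6 from 93.9% to 90.4%. Some statisticians prefer that level and others accept one-sided 5% for a single-arm product-performance study. That is a trade-off. The 90.4% belongs to a test that this trial does not plan, so it does not correct the stated 93%.

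**Conclusion.** No change follows. Followed as written, the plan gives a valid one-sided 5% test with its power correctly described, and a valid 95% interval for the size of the agreement. They answer different questions: the test asks whether the proportion exceeds 0.5, and the interval shows precision in both directions. A reader shown p = 0.039 beside 0.494 to 0.616 is correctly informed on both.

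The visible disagreement is confined to two or three counts, near 56% agreement. Its chance is 3.6% at the design alternative with n = 270. With an assumed neutral share of up to 20% it is 3.4% to 8.9%, and it is negligible once the true proportion reaches 0.65. The larger figures, 9.5% to 15.0%, need a true proportion of 0.55, which the documents nowhere assume.

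This rests on reading the primary interval as two-sided. If a one-sided limit was meant, it would already agree with the test and the question would not arise. Repeating the level in 6.5.10.2 or calling the interval descriptive would be tidy, but would alter no analysis, result or decision.

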6.5.10.3 Sensitivity Analyses

Sensitivity to missing primary endpoint data will be evaluated using best-case imputation, worst-case imputation, and tipping point analysis.

6.5.10.4 Secondary Efficacy

There are no predefined secondary effectiveness endpoints.

Page 18 of 44 – CONFIDENTIAL

6.5.10.5 Supportive Effectiveness Endpoints

6.5.10.5.1 Consumer Survey

Agreement with statements in the online consumer survey will be analyzed using the same method described for primary endpoint.

Subject listings for online consumer survey responses will be presented.

6.5.10.5.2 Investigator Questionnaire

The investigator questionnaire is collected at the Exit Visit. The responses to each statement in the investigator questionnaire will be summarized using categorical summary statistics and the percentages will be based on the number of subjects for whom there are non-missing responses.

The following investigator questionnaire items will also be evaluated using one-sided exact binomial test of the alternative hypothesis that the proportion of subjects for whom the investigators agreed is greater than 0.5.

- The proportion of subjects for whom the investigator was completely, very satisfied, or somewhat satisfied with the use of the contact lenses by the subject
- The proportion of subjects for whom the investigator agrees that the lens was easy to fit for the subject
- The proportion of subjects for whom the investigator agrees that the lenses deliver clear vision for the subject
- The proportion of subjects for whom the investigator agrees that the lens helps maintain a smooth, wettable surface for the subject
- The proportion of subjects for whom the investigator reports that it was extremely simple, simple, or somewhat simple to successfully fit the contact lens for the subject
- The proportion of subjects for whom the investigator agrees that the fitting process for the lens was straightforward for the subject
- The proportion of subjects for whom the investigator reports that it was extremely easy, easy, or somewhat easy to successfully fit the lens during the first visit for the subject

Subject listings for investigator questionnaire responses will be presented.

6.5.10.5.3 Number of Visits to Achieve a Successful fit

Study lens dispensation will be collected at the Screening/Dispensing Visit and 1-Week Follow-up Visit at the eye level. Subjects may require a change to their study lens power at the 1-Week Follow-up Visit. The total number of visits required to achieve a successful lens fit will be summarized for the FAS using continuous summary statistics.

Page 19 of 44 - CONFIDENTIAL

In addition, unscheduled lens replacements will be summarized categorically by replacement reason for completed eyes and discontinued eyes. Subject listings for visit accountability and unscheduled visits will be presented.

6.5.10.5.4 Number of Refinements to Achieve a Successful Fit

The number of refinements completed will be collected at Screening/Dispensing Visit and 1-Week Follow-up Visit (if subject requires a change to their study lens power at this visit) at eye level. Data will be summarized for the FAS as continuous summary statistics at the eye level. Refinements at the Screening/Dispensing Visit and the 1-Week Follow-up Visit will be summarized separately, and a combination of the two visits will be summarized as well.

The number of lens refinements at the Screening/Dispensing Visit will be summarized by baseline add groups using categorical summary statistics for the following categories: 1, 2, 3, >3 refinements. The summary will be at the eye level. Baseline add group is defined based on the add power obtained at the Screening/Dispensing Visit (> 1.50D as High Add, <= 1.50D as Low Add). A total column combining low add and high add will be summarized. Eyes with missing add will not be included in this analysis.

Starting lens sphere and add as well as final lens sphere and add for dispensed lenses at the Screening/Dispensing Visit will also be summarized by baseline add groups. If the subjects achieve plano status with their starting sphere and add for an eye, no final sphere and add will be collected and the starting sphere and add will be summarized as their final sphere and add.

If the subject requires a change to their study lenses at the 1-Week Follow-up Visit, then the final sphere and add at the Screening/Dispensing Visit and 1-Week Follow-up Visit will be summarized. An additional summary of final add on both eyes will be conducted by the following categories: Low add – Low add, Low add – None, Low add – High add, High add – High add – None. Percentages will be based on the number of subjects with non-missing responses for both eyes at each visit. Final sphere and add for this analysis are the final dispensed lens power that can provide satisfactory vision after the fitting procedure (final sphere and add for subjects whose starting sphere and add cannot achieve satisfactory vision and starting sphere and power for subjects who have satisfactory vision with starting lens power).

For eyes that require a change to their lenses, continuous summary statistics will be provided for sphere change and categorical summary statistics will be provided for add change using the following categories: Low Add to None, Low Add to High Add, None to Low Add, None to High Add, High Add to None, High Add to Low Add. The percentage of each add change

Page 20 of 44 - CONFIDENTIAL

category will be based on the number of eyes that require an add change. The lens change summary will be performed at the eye level for eyes that have: sphere change only, add change only, and both sphere and add change, and at subject level for subjects who have: sphere change only in both eyes, sphere change only in either eye, add change only in both eyes, add change only in either eye, sphere and add change in both eyes, sphere change in one eye and add change in the other eye, and sphere and add change in either eye. In addition, a shift table will be provided for subjects who have an add change in either eye, at the subject level.

A data listing for the number of refinements for each eye at each visit will also be presented.

6.5.10.5.5 Contact Lens Visual Acuity

Binocular distance, intermediate, and near high contrast lens VA (letters correct) with habitual lenses will be obtained at the Screening/Dispensing Visit. The binocular distance, intermediate, and near high contrast lens VA will be obtained for dispensed study lenses at the Screening/Dispensing Visit, and with worn study lenses (if the subject comes in wearing study lenses) or for dispensed study lenses (if the subject requires a change to their study lenses at 1-Week Follow-up Visit) at all follow-up visits. 90% High Contrast logMAR charts with Sloan Letters from Precision Vision, Inc. will be used for distance, intermediate, and near lens VA assessments.

For distance VA, letter scores obtained with distance VA chart (CAT. NO. 2103-2) will be converted to the logMAR scales using the following algorithm and rounding to two decimals:

If $X \ge 7$ then logMAR = 0.8 - (0.02*[X - 7]); Else if X < 3 then logMAR = 1.0 - 0.0333*X; Else if $3 \le X < 7$ then logMAR = 0.9 - (0.025*[X - 3]); Where X = the number of letters entered on the case report form.

This algorithm reflects the distance VA chart being used in this study, starting at the 20/160 Snellen line and with 3 letters on the first line, 4 letters on the second line, and 5 letters on each line thereafter. An example of the chart used for distance VA is as follows:

Page 21 of 44 - CONFIDENTIAL

Snellen	logMAR	Chart		Letters Correct
20/160	0.9	S Z	N	3
20/125	0.8	RN	CV	4
20/100	0.7	KCR	ΗN	5
20/80	0.6	ZKD	V C	5
20/63	0.5	ΗVΟ	R K	5
20/50	0.4	R H S	O N	5
20/40	0.3	OKSVZ	K S 🗙 R H	4
20/32	0.2	KSNHO	XXKXX	1
20/25	0.1	HOVSN	NDVKO	
20/20	0	VCSZH	DHOSZ	
20/16	-0.1	CZDVR	VRNDO	
20/12.5	-0.2	SHRZC	CZHKS	
20/10	-0.3	DNOKR	ORZSK	

Figure 1. Distance Visual Acuity (High Contrast) Example Chart

TOTAL 32

For intermediate and near VA, logMAR scoring is the same as distance VA but using different charts (CAT. NO. 2105 for intermediate VA and CAT. NO. 2107 for near VA), which both start at the 20/400 Snellen line and with 5 letters on each line. Letter scores obtained with corresponding charts will be converted to the logMAR scales using following algorithm and rounding to two decimals:

logMAR = 1.4 - (0.02*X)Where X = the number of letters entered on the case report form.

Binocular distance, intermediate, and near high contrast logMAR lens VA will be summarized separately by visit and visit type (unscheduled/scheduled) as continuous summary statistics. Only unscheduled visits in the visit window are included in unscheduled visit type for the corresponding visits. The average for each subject will be summarized if there are multiple unscheduled visits in the same visit window. A Total column will summarize the average for each subject over all scheduled and unscheduled visits. In addition to the summaries provided for each visit, a summary considering all study lens VA scores will be included and will be based on the average of all lens VA assessments for each subject, including VA at scheduled visits and unscheduled visits regardless of whether unscheduled visit happened in the scheduled visit window or not.

Change from binocular high contrast distance lens VA for dispensed study lens obtained at the Screening/Dispensing Visit will also be summarized for binocular high contrast distance

Page 22 of 44 - CONFIDENTIAL

logMAR lens VA at all Follow-up Visits and will be based on the average of all changes for each subject if there are multiple assessments in a visit category, similarly to the summary of binocular high contrast distance lens VA.

Binocular lens VA for habitual lens and study lens will also be summarized categorically (in Snellen equivalent feet) in both mutually exclusive and cumulative categories (ie, summarizing 20/20 or better, 20/25 or better, etc.) by visit. An additional summary of all study lens VA will be provided based on the worst case over all study lens VA assessments. Shift tables will be provided showing change from baseline in Snellen equivalent feet units to the final follow-up lens VA for study lenses.

Subject listings will be presented for binocular high contrast distance, intermediate, near lens VA with habitual lenses and study lenses, including letters correct, VA in logMAR and Snellen equivalent feet units.

6.5.10.5.6 Lens Performance Rating Scales

Lens performance data will be collected at Screening/Dispensing Visit for habitual lenses and at follow-up visits for the study lenses rating from 0 to 100 at the eye level. An abbreviated lens performance assessment for the study lens is conducted at the Screening/Dispensing Visit. Data from the lens performance rating scales will be summarized using continuous summary statistics by visit, including change from habitual lens for follow-up visits at the eye level and subject level. The average of scores for both eyes will be used when summarizing at the subject level. For each lens performance parameter, responses are categorized as favorable if the score \geq 50 and as unfavorable if the score < 50. A two-sided 95% confidence interval around the percentage with favorable responses will be presented by conducting a binomial (Clopper-Pearson) test. The p-values will be provided from a two-sided binomial test comparing the percentage of favorable responses to 50%.

Mean change from habitual lens performance ratings for each follow-up visit at the subject level will be compared to zero with an exploratory one-sided one-sample t-test by item. The alternative hypothesis will be that the mean change is greater than zero.

A subject listing of lens performance data for habitual lenses and study lenses will be presented.

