### **8.3 Source Documentation**

All medical information obtained at each study visit must be recorded in the subject's record (source documentation) in real time as it is collected. Source documentation consists of original subject documents, as well as data and records with information relevant to the subject and his/her participation in the study.

Examples of source documents include hospital records, clinical and office charts, laboratory notes, memoranda, signed ICFs, evaluation checklists, recorded data from automated instruments, copies or transcriptions certified after verification as being accurate copies, and information initially recorded in an electronic format. Source documentation worksheets may be provided by the Sponsor to record pertinent information.

Subject-completed forms are also considered to be source data. In no instance should an Investigator or study site personnel record any data or make changes to subject-completed forms. The Investigator or designee should review subject-completed forms during study visits for completeness and accuracy. If an entry is found to be illegible or a mistake is found (e.g., incorrect year was recorded), the subject should be instructed to edit the entry by drawing a single line through the original entry, entering the new information, and dating and initialing the change.

Subjects should be provided the rating scales (separate document) to use while responding to the lens performance assessments being collected. Enter rating from 0 to 100 (e.g., 90).

Source documentation worksheets may be provided by the Sponsor as a tool to record pertinent information. The completed worksheets can then be incorporated into the subject's medical chart. If it is preferred to not use the worksheets in the subject's permanent record, then the worksheets should be used as a reference to determine the type of study data to record in the subject's permanent record. The source document worksheets may be used as a supplement for the subject's medical records.

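### A lens-performance score of exactly 50, the midpoint of the 0–100 scale, is counted as favorable and tested against 50%, unlike neutral survey answers, which are left out of the test (minor, supportive analysis)

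*SAP*

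**What the plan says.** SAP 6.5.10.5.6 collects the ratings "at follow-up visits for the study lenses rating from 0 to 100 at the eye level". It then adds a dichotomy: "For each lens performance parameter, responses are categorized as favorable if the score" is at least 50, and "as unfavorable if the score < 50. A two-sided 95% confidence interval around the percentage with favorable responses will be presented". The interval is Clopper-Pearson. The test is specified as follows: "The p-values will be provided from a two-sided binomial test comparing the percentage of favorable responses to 50" percent. There is no neutral category, and no reason is given for placing 50 on the favorable side.

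The survey is handled differently. In SAP 6.5.10.2 the neutral answer is a category of its own and "will not be included in the primary statistical analysis". SAP 6.5.10.5.1 applies the same method to the other survey statements, and SAP 6.5.11.1 keeps neutral answers out of the missing-data sensitivity analyses.

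Protocol 7.1.3.6 plans only continuous summaries of the rating scales. The favorable/unfavorable cut and its test appear only in the SAP. They are not recorded under SAP 6.6 and are not in the Holm list of SAP 6.5.11.4.

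**The concern.** A 50% reference value represents indifference only if indifferent raters divide evenly between the two categories. Under this rule they do not: every score on the midpoint goes to the favorable side. If some subjects use 50 to mean no view either way, a sample with no net preference has an expected favorable rate above 50%, and the test can call it significantly favorable.

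In a single-arm, open-label study with no comparator, the 50% value is the only benchmark for this test, so its meaning matters. One report would also carry two kinds of favorable percentage, one from the survey with neutral answers removed and one from the ratings with midpoint answers counted for the product. The p-value is planned for each rating parameter, and ratings are collected at both follow-up visits.

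**Working it through.** **Inputs**
- n = 270 completers, with 300 enrolled as a check (SAP 6.5.13).
- Null value 50%, two-sided exact binomial test (SAP 6.5.10.5.6).
- Two-sided 5% level. The SAP states no level for this test, so this is assumed from the 95% interval.
- s, the share of scores at exactly 50. The documents do not give it. Assumed range 0% to 30%, with the remaining scores split evenly above and below 50.
- One score per subject. SAP 6.5.10.5.6 says "The average of scores for both eyes will be used when summarizing at the subject level", while SAP 6.5.10.1 calls for the worse eye for categorical variables. Under either rule, s is the share of subjects whose subject-level value is exactly 50.

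**The plan's own figure.** The plan states no power for the rating test. For the primary test it states 93% (one-sided 5%, 0.5 versus 0.6, n = 270). The exact test rejects from 150 agreements, with exact level 0.0387 and power 0.939, which agrees with the stated figure to within a point.

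**Rejection boundary of the rating test.** At n = 270, p = 0.059 at 151 favorable and p = 0.044 at 152. A significantly favorable result therefore needs at least 152/270 = 56.3%. At n = 300 it needs 168/300 = 56.0%.

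**Indifferent sample under the SAP rule.** The favorable rate is s + (1 − s)/2 = 0.5 + s/2. The chance of a significantly favorable result is the binomial upper tail at that rate:

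| s | favorable rate | n = 270 | n = 300 |
|---|---|---|---|
| 0% | 50.0% | 2.2% | 2.2% |
| 2% | 51.0% | 4.6% | 4.7% |
| 5% | 52.5% | 11.7% | 12.4% |
| 10% | 55.0% | 35.8% | 38.7% |
| 15% | 57.5% | 67.9% | 72.1% |
| 20% | 60.0% | 90.4% | 92.9% |

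The expected result reaches the n = 270 boundary when 0.5 + s/2 = 152/270, so s = 2 × 0.563 − 1 = 12.6%.

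**Two worked samples, n = 270**
- 121 above, 28 at 50 (10.4%), 121 below: 149/270 = 55.2%, p = 0.10. Not significant.
- 108 above, 54 at 50 (20%), 108 below: 162/270 = 60.0%, 95% CI 53.9% to 65.9%, p = 0.0012. Without the midpoint scores, 108/216 = 50%, p = 1.0.

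**No heaping at 50.** If ratings were spread evenly over the integers 0 to 100, the favorable rate would be 51/101 = 50.5% and the false-favorable rate about 3.2%. The effect therefore comes from answers gathering at 50.

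**Size of the excess in general.** Let p be the favorable share among scores other than 50. The SAP percentage is s + (1 − s)p. Excluding midpoints gives p, so the excess is s(1 − p). At p = 0.5 this is s/2. At p = 0.9 and s = 5% it is 0.05 × 0.1 = 0.5 percentage points.

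**Two possible repairs, n = 270**
- Leave exact 50s out of the test: the false-favorable rate is 2.1% to 2.3% for every s from 0% to 30% (two-sided error 4.2% to 4.5%).
- Count only scores above 50 as favorable but keep 50s in the denominator: the rate becomes 0.5 − s/2. The error moves to the other side, with 35.8% falsely unfavorable at s = 10%.

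**The case against.** The strongest reply is that nothing shown labels 50 as neutral. The rating scales are a separate document, whereas the survey has an explicitly worded neutral option. This stands: reading 50 as indifference rests only on its being the arithmetic midpoint.

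A second reply is that the size is conditional throughout. It needs both a sizeable share at exactly 50 and a sample otherwise balanced around 50. These are adapted multifocal wearers whose lenses are refined until vision is acceptable, so a sample centered on 50 is an extreme case. This also stands, and it limits the practical effect.

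A third reply is that the analysis is supportive. The continuous summaries, the change from habitual lenses and the listing do not depend on the cut. This is correct.

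A reader might go further in three ways that the documents do not support:
- *That the test is invalid.* As a test of whether half the scores are 50 or above, an exact binomial test holds its level. The difficulty is in reading the result as a preference.
- *That every favorable percentage is inflated by the full midpoint share.* The excess is s(1 − p) relative to excluding midpoints. It equals s only if midpoints stay in the denominator as non-favorable.
- *That the rating example in Protocol 8.3* ("Enter rating from 0 to 100 (e.g., 90") *pushes scores upward.* It sits in the source-documentation section, and nothing shows that it is printed on the subject's scale. If it did pull answers toward 90, fewer would fall at 50.

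None of this explains why the midpoint should count for the lens here when neutral survey answers are set aside.

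**Conclusion.** The point holds as a minor one. The coding gives every midpoint score to the favorable side and compares the result with 50%, which tilts the test in one direction and departs from the SAP's own handling of neutral survey answers.

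The false-favorable probabilities in the table assume that 50 means indifference, that the other scores are balanced around it, and a two-sided 5% level. They show what the rule permits and are not a forecast for this trial. If most ratings lie well above 50, both the excess and its effect on the conclusion are small.

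The primary endpoint and the tests in the Holm procedure are untouched.

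**What to change.** In SAP 6.5.10.5.6, define favorable as a score above 50 and unfavorable as a score below 50. Show exactly 50 as its own neutral row with its count. Compute the binomial test and the Clopper-Pearson interval on the scores other than 50, as SAP 6.5.10.2 does with neutral answers. Do not keep the 50s in the test denominator against an unchanged two-sided 50% null, because that only reverses the tilt. If the rating-scale document does anchor 50 as a favorable point, the SAP should cite it and still report the count at 50.

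The cost is one SAP sentence and one extra row in the affected tables, with no new data. The test denominator becomes slightly smaller (at s = 10%, 270 × 0.9 = 243), and the favorable percentages fall slightly, by s(1 − p).
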